#### 3.2 Setting of the study

This multicenter study will take place in four Dutch forensic psychiatric organizations that offer forensic psychiatric outpatient care: Stichting Transfore, Kairos, de Woenselse Poort and GGZ Noord-Holland Noord.

This study is initiated and will be coordinated by Stichting Transfore, an organization that has the goal to be frontrunner in developing and providing eHealth in forensic care. Transfore has participated actively on the development of multiple Minddistrict modules and other eHealth interventions. Additionally, Transfore has been conducting multiple implementation- and evaluation research, to – among other things – internet-based interventions. GGZ Noord-Holland-Noord started experimenting with internet therapy in 2001. Nowadays, multiple applications of eHealth are integrated in treatment methods. Together with other GGZ-providers, GGZ Noord-Holland-Noord developed multiple (forensic) modules for the Minddistrict platform. De Woenselse Poort is part of GGzE and is also a frontrunner on

innovation in (forensic) mental healthcare. Many of their projects are focused on eHealth: Minddistrict, mobile apps and virtual reality. Kairos is part of Pompestichting which has been inducting research on multiple areas for many years. Their main focus lies on technology and innovation, and other ways to improve treatment methods.

### 3.3 Overview of the study design

A schematic overview of the participant flow throughout the RCT, from screening up until follow-up assessment, is provided in Figure 1. The study design is briefly explained after the figure; a more detailed description of the procedure is provided in section 8.3.

The flow of the participants throughout the RCT is visualized in Figure 1. The first step, therapists will first **screen** the patients on suitability when they are first discussed in a 'multidisciplinary consultation' [multidisciplinair overleg; MDO]. Once the patient has been deemed suitable for participation, the therapists wait 8 weeks before **introducing** the study to the patient and asks for their consent to be contacted by a researcher. The main reason for not directly informing the patients during their intake or initial treatment sessions, is that patients already receive a lot of information at the beginning of their treatment, and thus often feel overwhelmed. Additionally, in practice, Minddistrict is often introduced later in the treatment process, because it often takes time to build a good therapeutic relationship, which is seen as a necessary requirement for starting with blended treatment, especially in a population known for its low treatment motivation.

If the patient agrees to be contacted by a researcher for further information about the study and possible inclusion, they will be contacted by phone, videoconferencing or in-person, depending on the preference of the patient. The researcher will inform them about participation and the consequences on being randomized to either the control or experimental condition. The researcher will clearly communicate that patients who are assigned to the control condition can still use an internet-based intervention after the study is finished. Furthermore, the researcher will clearly indicate that the decision to participate or drop out of the study will not affect their treatment or evaluation of their therapist. After informing the patient by means of a conversation and folder, the researcher will ask for their informed consent in participating. Next, the patient fills out the baseline assessment (T0) and is randomized to the control condition - which comprises forensic psychiatric treatment as usual (TAU) for aggression regulation, or the experimental condition, in which the internet-based intervention 'Aggression' is used as a supplement to TAU.

Patients will start with the Aggression module after approximately 12 weeks: this might exceed to a maximum of 14 weeks, if the patient for example is not able to start yet or misses several treatment sessions – which happens often in forensic mental healthcare. Participants are assessed four times throughout the study. They are first assessed at

[figure not shown]

baseline (T0), i.e. in week 12. A mid-treatment assessment (T1) is conducted when participants are supposed to be halfway throughout the internet-based intervention, i.e. 6 weeks after baseline, so in week 17. After completing the intervention, post-treatment assessment will be conducted. If participants complete a lesson per week, the intervention should be finished after 11 weeks. However, in practice, this often is not the case, for example because the patient misses treatment sessions or other psychosocial crises can arise that have priority. Consequently, post-treatment assessment will take place 14 weeks after baseline, i.e. in week 25. Finally, a follow-up assessment will be conducted. This assessment will take place 3 months after T2, so during week 37 of the entire study.

At all assessment points, patients will fill out three self-report questionnaires via Qualtrics: Regulatory Emotional Self-efficacy (RESE) scale [31], the Corrections Victoria Treatment Readiness Questionnaire (CVTRQ): a validated self-reported questionnaire [32], and the Dutch version of the Aggression Questionnaire (AVL-AV) [33, 34]. Participants in the experimental condition also fill out the the TWente Engagement with Ehealth and Technologies Scale (TWEETS) [35] at the beginning, halfway and at the end of the internet-based intervention Aggression. Furthermore, the scores of the risk assessment instrument 'Forensisch Ambulante Risico Evaluatie (FARE) [36] - which is part of standard procedures – will be used to assess change in dynamic risk factors in all participants .

Additionally, a qualitative interview study with 20 patients will be conducted to gain insight into their experiences, perceived positive and negative points, and points of improvements regarding the internet-based intervention. These participants will be randomly selected from the sample that started the experimental condition by means of a random number generator. These interviews will take place within 5 weeks after post-treatment assessment (T2), i.e. during week 25-30 of this study. Finally, all participating therapists will be sent an open-ended questionnaire to ask them similar questions about experiences, perceived positive and negative points, and points of improvements. These questionnaires will be send at the end of the data collection period, i.e. in Q2 2023.

Figure 1: Participant flow throughout the RCT

## 4. STUDY POPULATION

### 4.1 Population (base)

#### *Description of the population base*

Forensic mental healthcare is focused on people who display aggressive or sexual delinquent behaviour that led or could lead to offending and simultaneously suffer from at least one psychiatric disorder, for example schizophrenia, alcohol abuse, antisocial personality disorder or post-traumatic stress-disorder [1-3]. Due to this combination of offending and psychiatric disorders, forensic mental healthcare - or forensic psychiatry - takes place at the intersect of mental healthcare and the law. Forensic mental healthcare encompasses treatment of both in- and outpatients. Inpatients reside in clinics with different levels of security, ranging from very high levels, where patients are not or almost never allowed to go on leave, to medium or low levels, where patients have more freedom and independence [37]. While relatively many forensic psychiatric patients receive treatment at inpatient clinics, a large share of the patient population comprises outpatients who live at home and receive treatment at an outpatient clinic [38]. Some patients receive treatment voluntarily and not as part of a sentence, for example when a general practitioner refers them to forensic mental healthcare because it fits their aggression regulation problems better than regular mental healthcare. Regardless of the differences between security levels, the main goal of forensic mental healthcare is always to prevent (re)offending and thus to protect society. Treatment of forensic psychiatric patients is viewed as challenging, which can be partly explained by characteristics of the patient population: most forensic psychiatric patients are not that motivated for their treatment [4, 5]. Furthermore, they often have followed no or very little education and many patients have low literacy levels [6-8]. Additionally, co-morbidity is common: patients often have multiple psychiatric disorders [9]. In general, the forensic psychiatric patient population is very heterogeneous, but the main common factor is that for all patients, there is a risk on (re)offending.

This study is focused on people that receive forensic psychiatric outpatient care with a primary focus on aggression. To increase the feasibility and generalizability of this study, inclusion takes place at four large forensic psychiatric organizations that all treat patients at multiple outpatient clinics.

#### 4.2 Inclusion criteria

In order to be eligible to participate in this study, a subject must meet all of the following criteria:

- 1) The patient is 18 years or older
- 2) The patient is treated at an outpatient clinic
- 3) The patient receives one-on-one treatment
- 4) During the intake, improvement of aggression regulation has been selected as one of the treatment objectives
- 5) The patient indicates that they are able to read and write simple texts
- 6) The therapist responsible for treatment of the patient indicates that participating will not result in any harm for the patient
- 7) The patient voluntarily consents to participation

#### 4.3 Exclusion criteria

A potential subject who meets any of the following criteria will be excluded from participation in this study:

- 1) The patient has a current psychosis
- 2) The patient resides in any type of psychiatric inpatient clinic – this can be a forensic, but also another type of clinic
- 3) The patient receives group treatment focused on aggression regulation (specifically: AR [aggressieregulatie] op maat)
- 4) The patient is analphabetic, i.e. being unable to read and write
- 5) The responsible therapists identifies any other valid reason for exclusion

As can be seen in the in- and exclusion criteria, the responsible therapist is actively involved in determining whether participating in the study is safe and possible for the patient. This will first be discussed during the MDO. If, after several treatment sessions, the therapist identifies any reasons for exclusion, this will be communicated to the researcher and the patient will not be invited to participate.

Because the internet-based intervention 'Aggression' is transdiagnostic and is not focused on one psychiatric disorder, no psychiatric disorders were used to define the target group. This is also not feasible because forensic psychiatric patients are not enrolled in forensic mental healthcare for a diagnosis, but because of their delinquent behaviour. Additionally, many patients have multiple diagnosis: co-morbidity is relatively high in this target group. By keeping the in- and exclusion criteria relatively broad, patients from a large sample can be included, increasing the feasibility of this study.

#### 4.4 Sample size calculation

This sample size calculation is conservatively based on the ability to detect at least a moderate effect of Cohen's  $d = .50$  on the primary outcomes at follow-up (T3). A power analysis was conducted with G\*power. The analysis was conducted with a moderate effect size of 0.5, a  $\beta$ -power of .8, a p-value of 5%, and an independent two-sided t-test as method of analysis. This analysis showed that 64 patients need to be included in each condition. This means that a total of 128 patients needs to be included. Accounting for a drop-out of 20%, the goal for inclusion is set at a total of 154 patients. It is important to note that participants in the experimental condition are considered as a 'drop-out' when they don't fill out the questionnaires at all measuring moments, not when they stop using the intervention. In other words: patients can stop using the intervention. In other words: patients can stop using the intervention, but can still complete their participation in the study if they fill out all questionnaires. Adherence to the intervention is not the same as drop-out from the study, since it is a different concept. The main reason for this is that earlier research has shown that patients often stop using these interventions before all lessons are completed, so it is not realistic to expect that all patients fully complete the intervention. In order to account for this, the number of completed lessons will be included as a moderator for effectiveness in the analyses to investigate whether adherence is related to effectiveness. Additionally, a sub-goal of this study is to determine whether engagement is a predictor of adherence and effectiveness to incorporate non-adherence to the intervention in the study. The intended 154 patients will be included at four different organizations that all have multiple forensic outpatient clinics.

To the best of our knowledge, there are no other studies on the evaluation of internet-based interventions in forensic outpatient care. Consequently, the effect size of .50 is based on similar studies. A recent systematic review on internet-delivered CBT for depression and anxiety disorders identified a mean effect size of .80 at follow-up after 3 to 36 months when looking at the post-test difference between treatment and control conditions [39]. However, in forensic mental healthcare, lower effect sizes are expected due to the complexity of improving treatment outcomes in this population. To illustrate: CBT appears to be more effective for treatment of specific disorders such as anxiety or depression than for treatment of aggression [13, 14]. Consequently, the more moderate effect size of the current RCT is set on .5.

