### **8.6 Replacement of individual subjects after withdrawal**

To account for withdrawal of subjects, 20% more participants than required according to the power analysis will be included. If patients drop-out, this will be accounted for due to this extra 20%. Patients are considered as a drop-out if they stop filling out the questionnaires before the end of the study. Consequently, if patients stop using the intervention but still fill out the questionnaire, they are not considered a drop-out. A reason for this is that investigating whether non-adherence to these interventions is problematic and related to engagement or effectiveness is part of this study. Data collection will be ended after including the intended 154 patients. If throughout the study, there are signs that more than 20% of the patients drop out, the researchers will re-evaluate the feasibility of the data collection with participating therapists and search for points of improvements.

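### The 20% drop-out allowance was added to 128 instead of divided out: 154 enrolled leaves about 123 patients, not the required 128, and covers only 16.9% drop-out

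*Combined protocol and SAP*

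**What the plan says.** Section 4.4 bases the sample size on the primary outcomes at follow-up (T3): "The analysis was conducted with a moderate effect size of 0.5", 80% power, and "a p-value of 5%, and an independent two-sided t-test as method of analysis". The result is given as "This analysis showed that 64 patients need to be included in each condition" and "This means that a total of 128 patients needs to be included". The allowance for losses follows: "Accounting for a drop-out of 20%, the goal for inclusion is set at a total of 154 patients".

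Section 8.6 explains the allowance as "20% more participants than required according to the power analysis will be included" and says that this surplus will absorb the drop-outs. It also says that if more than 20% of patients appear to be dropping out, the researchers will reconsider the feasibility of data collection and look for improvements. Enrolment is capped: "Data collection will be ended after including the intended 154 patients".

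**The concern.** Section 4.4 and the threshold in 8.6 both use 20% as a share of the patients enrolled. The inflation, however, takes 20% of the patients needed at the end. The two denominators differ, so a surplus of 20% on top of 128 cannot absorb a loss of 20% from 154.

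Two things are at stake. First, the enrolment target does not deliver the plan's own requirement under the plan's own drop-out assumption. Second, the threshold in 8.6 inherits the same figure: drop-out between roughly 17% and 20% already takes the trial below 128 without prompting any re-evaluation.

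**Working it through.** **Inputs.** From section 4.4: d = 0.5, two-sided α = 0.05, power 0.80, independent t-test, two equal arms, 64 per arm (128 in total), drop-out 20%, target 154. From section 8.6: the surplus is 20% of the required number, inclusion ends at 154, and re-evaluation follows above 20% drop-out.

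**1. The base figure reproduces.** The noncentral-t solution for these inputs is 63.77 per arm, rounded up to 64. Power is 79.5% with 63 per arm and 80.1% with 64. So 128 is correct.

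**2. The stated target reproduces only with the additive rule.**
- Required × (1 + drop-out): 128 × 1.20 = 153.6, rounded to 154. This matches the plan.
- Required / (1 − drop-out): 128 / 0.80 = 160, or 80 per arm. This does not match, by 160 − 154 = 6 patients.

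**3. What 154 leaves at 20% drop-out.** 154 × 0.80 = 123.2, about 123 patients. The shortfall is 128 − 123 = 5. By contrast, 160 × 0.80 = 128 exactly.

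**4. What drop-out 154 does cover.** 1 − 128/154 = 26/154 = 16.9%.

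**5. Power after drop-out** (same t-test, d = 0.5, two-sided 0.05):

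| Patients at T3 | Per arm | Power |
|---|---|---|
| 128 | 64 / 64 | 80.1% |
| 123 | 61 / 62 | 78.5% |
| 123.2 (unrounded) | 61.6 / 61.6 | 78.6% |

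The loss is about 1.6 percentage points. Put differently, with 61 and 62 patients 80% power is reached at d = 0.509 instead of 0.50.

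**6. Chance of ending below 128.** Assume, as an illustration that is not in the plan, that each patient drops out independently with probability 0.20. The binomial probability of fewer than 128 remaining is then about 81% with 154 enrolled and about 45% with 160.

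**The case against.** The arithmetic is hard to dispute, so the serious objections concern its importance.

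- **The effect is very small.** A 1.6-point loss of power equals an error of about 0.01 in the assumed effect size. Section 4.4 chose d = 0.5 by judgement, scaled down from 0.80 in a different population, so its uncertainty is far larger than that. This stands, and it limits the weight of the point.
- **The main analysis is a mixed model that uses partial data (section 10.1).** Section 4.4 defines a drop-out by failure to complete the questionnaires at all measuring moments. That can be read to include someone who misses T1 but answers T3, and such a patient still contributes. This stands in part: it softens the loss by an amount the documents do not allow one to quantify. But the sample size rests on a t-test at T3, and the model does not restore T3 observations that were never made. In the other direction, section 8.7 excludes patients who leave treatment altogether, and the 20% is not said to cover them.
- **The threshold in 8.6 is a soft prompt.** It adds no patients, and the reminders and vouchers operate from the start whatever the drop-out rate. True, so moving it will not by itself protect the sample. It is still set at a level where the requirement has already been missed.
- **Section 8.8 already accepts analysis below the intended number if funding ends.** That concerns stopping early. It does not make 154 the right figure for a trial that recruits in full.

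A reading of 20% as a share of 128 would make the surplus self-consistent, but it conflicts with 8.6, which speaks of the proportion of patients who drop out.

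**Conclusion.** The concern holds. The required 128 is right; the step from 128 to 154 is wrong. At the plan's own 20% drop-out, 154 enrolled leaves about 123 patients and about 78.5% power for the stated test. The target is 6 patients below the consistent figure of 160, and it covers 16.9% drop-out.

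The conclusion assumes that 20% means a share of enrolled patients, as section 8.6 uses it, that losses fall about equally on the two arms, and that the t-test at T3 is the basis for power, as section 4.4 says. The consequence is minor and does not threaten the trial's validity, but the plan makes a claim about its size that its own numbers contradict, and it should be corrected.

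**What to change.** Correct sections 4.4 and 8.6 in one of two ways.

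1. **Keep 154 and restate what it covers.** Say that 154 allows for about 16.9% drop-out, or that 20% drop-out would leave about 123 patients at T3 and about 78.5% power for d = 0.5. In 8.6, remove the claim that the extra 20% covers a 20% loss and set the re-evaluation threshold at about 17%. This costs a few sentences and no extra patients; the stated figure becomes slightly less favourable.
2. **Keep 80% power and 20% drop-out.** Set the target at 160 (80 per arm) wherever 154 appears in 4.4 and 8.6, leave the 20% threshold as it is, and change the figure in section 4.5 from about 38 patients per organisation to 160 / 4 = 40. This costs 6 more patients.

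Under either option, add one sentence saying whether the drop-out allowance includes patients excluded under 8.7 for leaving treatment.
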